#### Analysis of the Secondary Outcome Variables for Efficacy:

The secondary outcome variables for efficacy include: relaxation following maximum voluntary isometric contraction of the long finger flexors, repetitive stimulation relaxation time, rapid hand contraction and extension time, composite MVICT score derived by averaging the standardized (normalized) scores across the 10 individual muscles, grip strength derived by averaging the strength scores over the left and right hands, average MMT score derived by averaging the individual MMT scores across the 26 individual muscles, DEXA lean body mass, Modified Chronic Pain Scale scores, Brief Pain Inventory scores, holter monitor findings, IBS-IS scores, GSRS-IBS score, swallowing times, Purdue pegboard score, time to rise from a chair, time to walk 30 feet, Holter monitor data, SF-36 scores, and disease-specific health-related quality-of-life scores. These variables will be analyzed as described above for the primary outcome variable using repeated measures analysis of covariance, with the baseline value of the outcome variable used as a covariate. Again, depending on the nature of the outcome variable, data transformation or the use of nonparametric statistical methods may be required for analysis.

#### Analysis of Safety Outcomes and Subject Disposition:

Adverse events will be tabulated by treatment group, severity, and perceived relationship to study drug. For each adverse event (AE), the treatment groups will be compared regarding the occurrence of at least one event using Fisher's exact tests. The comparisons will be repeated excluding all mild symptoms. Particular attention will be paid to AEs known to be associated with mexiletine in previous studies. Individual AEs will be listed, with particular attention paid to serious AEs. Laboratory test abnormalities will be similarly analyzed, whether or not they are judged to be clinically significant (classified as AEs).

Continuous measures of safety (vital signs, EKG results, laboratory test results) will be analyzed descriptively. Formal analyses may be performed using methods similar to those described above for the primary outcome variable (repeated measures analysis of covariance).

The frequency of and reasons for subject withdrawal, dosage reduction, and premature withdrawal of study drug will be summarized by treatment group. The compliance data (amount of unused drug returned, compliance diaries) will be summarized by treatment group and visit, as will dosage level of study drug. Guessed treatment from the blindness questionnaire will be tabulated by actual treatment separately for subjects and the investigator. Chi-square tests will be used to determine whether or not the proportion of subjects who guess that the subject received mexiletine treatment differ among the actual treatment groups. The investigator's guesses will be similarly analyzed. Additional information regarding adverse event assessment and processing is provided in the Human Subjects Protection portion of this application.

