### **APPROPRIATENESS FOR ORPHAN PRODUCT DEVELOPMENT GRANT PROGRAM:**

This study is being considered for funding by the FDA Orphan Product Development Grant Program. It is appropriate for this program for the following reasons:

- 1) Myotonic dystrophy type-1 is an orphan disease. The prevalence of DM1 is approximately one out of every 10,000 people worldwide. Based on this estimate, there are fewer than 100,000 cases of DM1 in the United States. Additional reports confirm the rarity of this disease noting prevalence of DM1 ranging from 2.4/100,000 in Northern Ireland, 5.5/100,000 in West Germany, and 4.9/100,000 in Switzerland.
- 2) Mexiletine is available on the market for the treatment of cardiac arrhythmias, but it is not currently approved for the treatment of myotonia or myotonic dystrophy.

3) This study will provide data on the long term (6 months) safety and efficacy of mexiletine in: a) improving the distance participants are able to walk in six minutes; b) reducing myotonia; c) improving muscle strength; d) increasing lean muscle mass; e) decreasing musculoskeletal pain; f) improving gastrointestinal function and swallowing); g) improving functional abilities; h) decreasing cardiac arrhythmias; and, i) improving disease-specific health related quality-of-life as measured by a novel multi-domain instrument.

If the safety and long term effectiveness of mexiletine is demonstrated, we anticipate that these results may lead to the approval of mexiletine as an orphan therapy for DM1.

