### **Study Testing Procedures:**

#### Evaluation of safety and tolerability:

Adverse side effects will be monitored during each CRC visit (Baseline, Month 3, Month 6) and during telephone calls at about 2 week intervals during the intervening weeks of the trial. The adverse effects of mexiletine observed most commonly include: dizziness, lightheadedness, nervousness, nausea, vomiting, or upset stomach, diarrhea, constipation, trembling, shaking of hands, blurred vision, tiredness, or weakness. More serious side effects, which are less common include: irregular heart beat, chest pain, shortness of breath, trouble breathing, skin rash, severe itching, or hives.

If there are more serious side effects, the principal investigator will be notified. The principal investigator will contact the patient and determine if it is necessary to have the patient reduce the dosage of treatment agent or to stop it. The principal investigator will also determine if an urgent evaluation of the patient is necessary. These medical plans and any related change in care will be coordinated with the primary care physician of the patient. If necessary, the code will be broken to determine if the patient is receiving placebo or mexiletine treatment.

Additional details regarding the evaluation of the safety and tolerability of this medication are provided in the human subjects section of this application.

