### 3. Potential Risks:

The risk category of this study is greater than minimal.

Mexiletine is approved by the FDA as an alternative treatment for symptomatic ventricular arrhythmias. The dosage selected for use in this study is in the low therapeutic range. Toxic side effects of mexiletine occur with greater frequency at higher dosages required to control arrhythmias and neuropathic pain. These dosages are typically two to three times higher than the dosages used in the present study. Patients taking these higher dosages of mexiletine (600-3200 mg/day) have a significantly increased incidence of upper gastrointestinal distress, 41%, lightheadedness and tremor, 12.5%. These symptoms are dose related, generally not serious, and disappear after dose reduction or discontinuation of treatment. No patient in our study will receive a dose of mexiletine greater than 450 mg a day.

A recent study which included 9 patients with DM1 has demonstrated that the relatively low dosage of mexiletine proposed for use in the present study is effective and has greater efficacy than other commonly used antimyotonia drugs, such as, dilantin, disopyramide, and tocainide. In addition, there were no severe side effects, worsening of heart block, or worsening of bundle branch block in our previous mexiletine crossover study of DM1 patients evaluating two low to moderate dosages [150 mg three times daily and 200 mg three times daily].

We anticipate that treatment with mexiletine will reduce or eliminate myotonia in our patients, and that they will experience few if any side effects at the dosage we have proposed.

There is a small risk of bruising from blood draws and muscle soreness from the quantitative myometry (QMT), manual muscle testing (MMT), maximum voluntary isometric contraction testing, and functional tests. Dual energy x-ray absorptiometry (DEXA) uses 0.5-1.0 mREM which is only a fraction of that used in a routine chest x-ray (20-30mREM) and is considered to pose to significant risk. There is minimal risk of transient discomfort from direct irritation to the nerve associated with the electrical stimulation during the repetitive stimulation test (measuring duration of myotonia).

Questionnaires, although we believe their content is benign, may produce mild emotional stress.

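### Clinical adverse events are compared between arms only by per-event Fisher tests, with no risk difference or interval, so at 20 per arm a non-significant result cannot support a safety conclusion

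*Combined protocol and SAP*

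**What the plan says.** Under Analysis of Safety Outcomes and Subject Disposition, the between-arm rule for clinical adverse events is: "For each adverse event (AE), the treatment groups will be compared regarding the occurrence of at least one event using Fisher's exact tests". It has one variation: "The comparisons will be repeated excluding all mild symptoms". The rest of the adverse event plan is tabulation by arm, severity and perceived relationship, plus individual listings. No risk difference, confidence interval or significance level is given for these comparisons. For the primary efficacy outcome, by contrast, Statistical Analyses specifies a 95% confidence interval for the treatment effect at Month 6.

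The documents describe the safety goal in several ways. Secondary Aims speaks of monitoring safety and tolerability. The last paragraph before Research Design and Methods says the study will determine efficacy, tolerability and safety. The orphan grant section makes a possible approval conditional: "If the safety and long term effectiveness of mexiletine is demonstrated".

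Potential Risks gives the only numerical side effect rates, in per cent: "upper gastrointestinal distress, 41%, lightheadedness and tremor, 12.5". They belong to patients on 600 to 3200 mg/day. The same section caps this trial at 450 mg/day. No placebo rates are given.

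**The concern.** A per-event p-value answers whether the arms differ beyond chance. It does not say how large a harm the data still allow, and with 20 patients per arm that is the more useful question. If the p-value is the only inferential output for clinical events, a reader of the final report has little to go on except the absence of significance. With tests this weak, absence of significance is the likely result even when the excess is substantial. At stake is what the trial can properly conclude about tolerability over six months, which is one of its stated purposes and is linked to a possible approval.

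**Working it through.** **Inputs.** 20 per arm, 1:1 (Trial Design). Rates of 41% and 12.5% (Potential Risks, for 600 to 3200 mg/day). Placebo rates are not in the documents, so they are assumed and varied from 0% to 20%. A two-sided 5% level is also assumed; the sample size section states that level for the secondary efficacy t-tests, but nothing is stated for safety.

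**The plan's own figure.** No power or precision is stated for safety, and the sample size comes from the six minute walk. A two-sample t-test with 18 per group, difference 183 feet and SD 190 feet has power 80.2% at two-sided 5%, and 18/(1 - 0.10) = 20. The stated 80% and 20 per group reproduce. They carry no information about adverse events.

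**Fisher threshold with no placebo events.** The two-sided p-value is 2 x C(20,k)/C(40,k).
- k = 4: 2 x 4845/91390 = 0.106.
- k = 5: 2 x 15504/658008 = 0.047.

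So at least 5 of 20 mexiletine patients must have the event. With a true rate of 12.5%, P(X >= 5) = 0.095, so the event is missed 90.5% of the time. With 41%, P(X >= 5) = 0.958, so it is missed 4.2% of the time.

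**Other placebo rates.** Power is the sum over all 21 x 21 tables of Bin(x; 20, p1) x Bin(y; 20, p0), counting tables with Fisher p <= 0.05. Miss rate is 1 minus power.

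| Placebo rate | Miss, 41% on mexiletine | Miss, 12.5% on mexiletine |
|---|---|---|
| 0% | 4% | 90.5% |
| 5% | 26% | 96% |
| 10% | 48% | 98% |
| 15% | 66% | not an excess |
| 20% | 79% | not an excess |

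With 18 per arm, the 41% column becomes 8%, 33%, 55%, 71% and 82%, and 12.5% v 0% is missed 93.5% of the time. One-sided testing at 5% lowers the miss for 41% v 10% to about 35% and leaves the 12.5% event missed more than 90% of the time.

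**Lower rates.** Power is 17% for 20% v 5% (against 74% for 41% v 5%) and 14% for 25% v 10% (against 52% for 41% v 10%).

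**What an interval adds.** Take 6/20 v 2/20, a difference of 20 points with Fisher p=0.24. The Wilson 95% limits are 14.5% to 51.9% for 6/20 and 2.8% to 30.1% for 2/20. The Newcombe limits are:
- lower: 0.20 - sqrt((0.300 - 0.145)^2 + (0.301 - 0.100)^2) = 0.20 - 0.254 = -0.05
- upper: 0.20 + sqrt((0.519 - 0.300)^2 + (0.100 - 0.028)^2) = 0.20 + 0.231 = +0.43

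The p-value alone hides that an excess of up to 43 points is compatible with these data. Even 0/20 v 0/20 gives -16 to +16 points.

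**The case against.** The strongest defence is that a 40-patient trial cannot be powered for safety and that this plan never equates p>0.05 with safety. That is correct. A reader might infer that the protocol promises to demonstrate safety by non-significance, but the orphan grant wording is conditional and the secondary aim is to monitor. Only the closing paragraph of Preliminary Studies says determine. The listings of serious events and the data safety monitoring board's review of imbalances also contribute to the safety judgement. None of them, however, puts an interval on a clinical event.

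A reader might also infer that this is the only formal safety comparison in the plan. It is not. "Laboratory test abnormalities will be similarly analyzed, whether or not they are judged to be clinically significant (classified as AEs"). For vital signs, EKG and laboratory values, "Formal analyses may be performed using methods similar to those described above for the primary outcome variable (repeated measures analysis of covariance"). Holter data, the two gastrointestinal scales and the quality-of-life scores are listed under secondary efficacy, where "These variables will be analyzed as described above for the primary outcome variable using repeated measures analysis of covariance"; that model yields 95% intervals. The gap is confined to clinical adverse events.

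Two readings of the numbers also go too far. One is to take a miss rate of about half as a floor for the 41% event: that needs a placebo rate near 10%, and with no placebo events the miss is 4%. The other is to treat 41% and 12.5% as the rates expected here: they come from higher doses, and the protocol expects few side effects at its own dose. Lower rates weaken the tests further, so the dose difference does not rescue them.

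Finally, the list of known effects ("dizziness, lightheadedness, nervousness, nausea, vomiting, or upset stomach, diarrhea, constipation") might suggest that testing related terms separately costs much power. The documents do not say how terms will be coded. In a simulation splitting a 41% upper gastrointestinal rate over three terms, with assumed placebo rates of 10% to 20%, at least one term was significant 17% to 48% of the time without multiplicity control, against 21% to 51% for the grouped outcome. That difference is too small to carry the point.

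It is also fair that intervals add no power and could be computed later from the tabulated counts. Specifying them in advance still settles what the safety conclusion will rest on.

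**Conclusion.** The point holds for clinical adverse events. Their only planned between-arm inference is a per-event Fisher test without an effect estimate or interval. A 12.5% event is missed at least 90% of the time. A 41% event is missed between 4% and 79% of the time, depending on a placebo rate that the documents do not give. These figures assume 20 analysed per arm and a two-sided 5% level, and they use rates quoted for doses above this trial's maximum. A non-significant comparison therefore cannot support a safety conclusion, and the plan does not specify the quantity that could show how much harm remains possible. This is a cheap improvement to the analysis and its reporting; it is not a flaw in the design or in the primary analysis.

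**What to change.** In Analysis of Safety Outcomes and Subject Disposition, for each adverse event and for any serious adverse event:

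1. Report the mexiletine minus placebo difference in the proportion of patients with at least one event, with a 95% confidence interval (for example Newcombe).
2. Keep the Fisher p-value as supplementary.
3. State that p>0.05 will not be taken as evidence of safety and that the safety conclusion will quote the upper bound of the excess risk.

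Grouping related terms into classes fixed before unblinding is an optional supportive summary.

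The cost is a few lines of text and one extra table, with no new data. The downside is a less favourable safety statement, because the intervals will be wide.

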#### Sample Size Considerations:

The primary outcome variable in this clinical trial will be the change from baseline to Month 6 in the mean distance walked during the six minute walk test. Using historical six minute walk test data in the DM1 population, we will have 80% power to detect a group mean change of 183 feet in distance walked over six minutes. This is based on a sample size of 18 per group (increased to 20 to account for the possibility of a 10% withdrawal rate), and a standard deviation of 190 feet. A two-sample T-Test Power Analysis is provided in Appendix A.

An important secondary outcome variable is the change from baseline to Month 6 in the time for relaxation of grip force following maximum voluntary isometric contraction of the long finger flexors.

This will be operationally defined as the time required to go from 90% of MVC to 5% of MVC averaged over three trials. In our randomized cross-over trials of mexiletine 150 mg three times daily and 200 mg three times daily, relaxation time from 90% to 5% of MVC was found to be the most sensitive measure of myotonia in terms of detecting a benefit of mexiletine. In the 18 subjects who completed the trial of 200 mg TID, the mean ( $\pm$  standard deviation) change (mexiletine – placebo) in this outcome was  $-1.34 \pm 1.42$  seconds. These data suggest that a sample size of 20 subjects per group will

provide 82% power to detect a group difference in mean response of -1.3 seconds in the proposed trial, using a t-test and a significance level of 5% (two-tailed).

Another important secondary outcome variable is the change from baseline to Month 6 in grip strength, averaged over the left and right hands. In our pilot randomized trial of troglitazone, grip strength data were available from 17 of the 20 randomized subjects at baseline and Month 8. The mean change averaged over both hands was -0.93 kg (reflecting mean changes of -1.32 kg in the left hand and -0.53 kg in the right hand) and the standard deviation of the changes was approximately 2.5 kg. Similar results were obtained at the Month 4 visit. These data suggest that a sample size of 20 subjects per group will provide 80% power to detect a group difference in mean response of 2.3 kg in the proposed trial, using a t-test and a significance level of 5% (two-tailed).

The sample size will be increased as necessary to achieve a final group of 20 DM1 patients in both the mexiletine and placebo treatment groups. We anticipate that there may be a 10% rate of subject withdrawal based upon our recently completed FDA funded, 7 week, double-blind crossover trial of mexiletine in DM1 [Appendix A].

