## **STUDY PROTOCOL**

**A Randomized, Placebo Controlled, Clinical Efficacy Trial of Mexiletine for Myotonic Dystrophy Type-1 (DM1).**

## **A Randomized, Placebo Controlled, Clinical Efficacy Trial of Mexiletine for Myotonic Dystrophy Type-1 (DM1).**

### **RESEARCH PLAN**

#### **A. SPECIFIC AIMS:**

**To evaluate the efficacy, tolerability, and safety of mexiletine in DM1 we will perform a six month, randomized, double-blind, trial of mexiletine (150 mg three times daily, n=20) vs. placebo (n=20) in ambulatory DM1 patients and pursue the Aims listed below.**

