## D. RESEARCH DESIGN AND METHODS:

### TRIAL DESIGN:

#### SCHEMATIC SUMMARY OF MEXILETINE TREATMENT IN DM1

This FDA Orphan Product Development Project proposes a double-blind, randomized, placebo-controlled, six month clinical trial of the efficacy and safety of mexiletine (150 mg three times daily) for the treatment of moderately affected ambulatory patients with DM1. Twenty patients will be randomized to receive treatment while another 20 patients will receive placebo. Patients will be randomized in a 1:1 ratio to receive either mexiletine (150 mg three times daily) or placebo. The primary outcome measure will be the assessment of ambulation by six minute walk time. Secondary outcome measures will include: a) grip myotonia as determined by relaxation time following maximum voluntary isometric contraction of the finger flexor muscles; b) muscle strength; c) change in lean muscle mass; d) pain measurement using the Brief Pain Inventory and a

modified Chronic Pain Scale; e) Gastrointestinal function measured by two gastrointestinal questionnaires; f) The ability to swallow as measured by a timed swallowing test with water; g) physical function as measured by the time to rise from a chair, Purdue Peg Board Score, time to walk 30 feet, six minute walk, and SF-36; and, h) pulmonary function (measured by serial determinations of forced vital capacity); i) change in Holter monitor data from baseline; and j) patient relevance as measured by a novel disease-specific health-related quality-of-life instrument designed specifically as an clinical outcome measure for the DM1 population.

During the trial of treatment with mexiletine, all patients will receive careful safety monitoring, including serial EKGs, laboratory testing, three in-person evaluations on the University of Rochester NIH funded Clinical Translational Sciences Institute sponsored Clinical Research Center, and phone calls to assess for any side effects or problems with the study medications, to encourage adherence to the treatment regimen, and to grade musculoskeletal pain. Below is a more detailed description of the study design and the outcome measures.

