One of the benefits of studying DM1 patients is that the diagnosis can be definitively established. DM1 is an autosomal dominantly inherited disease and it results from an unstable trinucleotide repeat,  $[CTG]_n$ , expansion in the DM gene on chromosome 19. The gene defect is well characterized and a specific diagnostic test using leukocyte DNA analysis is available to identify the abnormal enlargement of the  $[CTG]_n$  repeat and to identify affected individuals. The availability of a standard diagnostic test for DM1 assures us that all the patients in our study population have a family history DM1.

There will be 40 subjects with myotonic dystrophy between 18-80 years of age enrolled for this clinical trial. Up to 60 patients will be screened for this trial until accrual of 40 patients is met. Every effort will be made to insure that the study population reflects the makeup of the general population, including women and minorities, from which it is drawn.

For over 30 years in our Neuromuscular Disease Center we have provided care to a large population of DM1 patients, and over the past 25 years we have carried out clinical investigations to clarify the pathomechanism of the muscle wasting that occurs in these patients. We have also performed multiple therapeutic trials in subgroups of these DM1 patients. At present we have a funded NIH study to investigate the disease progression of DM1. This study has provided us with access to many patients from our local area and from other regions of the United States. It is possible that these patients may also wish to participate in our therapeutic trial. We also have access to over 580 DM1 patients through the National Registry of Myotonic Dystrophy Patients. We anticipate having no significant difficulty in recruiting the required number of patients for this trial.

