### **Targeted/Planned Enrollment**

**TABLE 3:**

#### **Targeted/Planned Enrollment Table**

**Study Title:** A Randomized, Placebo Controlled, Clinical Efficacy Trial of Mexiletine for Myotonic Dystrophy Type-1 (DM1).  
**Total Planned Enrollment:** 60 myotonic dystrophy patients

TARGETED/PLANNED ENROLLMENT: Number of Subjects			
Ethnic Category	Sex/Gender		
	Females	Males	Total
Hispanic or Latino	2	2	4
Not Hispanic or Latino	28	28	56
Ethnic Category: Total of All Subjects *	30	30	60
Racial Categories			
American Indian/Alaska Native	0	0	0
Asian	2	1	3
Native Hawaiian or Other Pacific Islander	0	0	0
Black or African American	4	4	8
White	24	25	49
Racial Categories: Total of All Subjects *	30	30	60

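### Two incompatible enrolment rules: the power quoted for the two important secondary outcomes needs 20 per arm to remain, but accrual of 40 with the plan's own 10% loss leaves 18

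*Combined protocol and SAP*

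**What the plan says.** **Number of patients.** The Specific Aims describe a "trial of mexiletine (150 mg three times daily, n=20) vs. placebo (n=20) in ambulatory DM1 patients". The Trial Design summary says "Twenty patients will be randomized to receive treatment while another 20 patients will receive placebo". Study Population gives the stopping point: "Up to 60 patients will be screened for this trial until accrual of 40 patients is met".

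**Primary outcome (Sample Size Considerations).** The plan claims 80% power for 183 feet with a standard deviation of 190 feet: "This is based on a sample size of 18 per group (increased to 20 to account for the possibility of a 10% withdrawal rate".

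**Two important secondary outcomes (same section).** Both use 20 per group with no allowance for loss.
- Relaxation time: 20 per group will "provide 82% power to detect a group difference in mean response of -1.3 seconds in the proposed trial". The standard deviation comes from the earlier crossover result of −1.34 ± 1.42 seconds.
- Grip strength: a "sample size of 20 subjects per group will provide 80% power to detect a group difference in mean response of 2.3 kg", with a standard deviation of approximately 2.5 kg.

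**Closing paragraph of that section.** "The sample size will be increased as necessary to achieve a final group of 20 DM1 patients" in both groups. No number or cap is given, and 10% withdrawal is cited again.

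**Table 3 (Targeted/Planned Enrollment).** The total planned enrolment is given as "60 myotonic dystrophy patients".

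**The concern.** The same 20 per arm has two meanings. In the accrual statement and the primary power statement it is the number randomised, from which 18 are expected to remain. In the closing paragraph of Sample Size Considerations it is the number who must remain, so more than 20 per arm have to be randomised. Both cannot govern.

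The conflict reaches the power statements because the primary is calculated after withdrawal and the two secondary outcomes before it. If accrual stops at 40, the secondary statements rest on patients whom the plan expects to lose. If the sample is enlarged, those statements stand, but the enrolment number in three other sections is too low. The number randomised also fixes the randomisation list, drug packaging and patient exposure, so it should be readable from the protocol without interpretation.

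**Working it through.** **Inputs.** All come from Sample Size Considerations: two-sample t-test, two-sided 5%; walk 183 ft, SD 190; relaxation time 1.3 s, SD 1.42; grip 2.3 kg, SD 2.5; withdrawal 10%. Trial Design gives 1:1 allocation. The printed SDs are taken as given.

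**Formula.** With n per arm, noncentrality is (difference/SD) × √(n/2), with 2n − 2 degrees of freedom. Power is the probability that the noncentral t exceeds the two-sided 5% critical value (2.032 at n = 18, 2.024 at n = 20).

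**Step 1: reproduce the primary.** 183/190 = 0.963. At n = 18 the noncentrality is 0.963 × 3 = 2.89 and power is 80.2%, as stated. The inflation also reproduces: 18/0.9 = 20.

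**Step 2: reproduce the secondary figures at n = 20.**
- Relaxation: 1.3/1.42 = 0.9155; × √10 = 2.895; power 80.5% (printed 82%).
- Grip: 2.3/2.5 = 0.92; × √10 = 2.909; power 80.9% (printed 80%).

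Differences that print as 1.3 s (1.25 to 1.35) give 77.4% to 83.4%, so 82% is within rounding. Neither printed power is an arithmetic error at its own n.

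**Step 3: the same calculation at n = 18.**
- Relaxation: 0.9155 × 3 = 2.746; power 76.1%.
- Grip: 0.92 × 3 = 2.760; power 76.5%.

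| Outcome | Printed | 20 per arm remain | 18 per arm remain |
|---|---|---|---|
| Walk, 183 ft | 80% (n = 18) | 84.3% | 80.2% |
| Relaxation, 1.3 s | 82% (n = 20) | 80.5% | 76.1% |
| Grip, 2.3 kg | 80% (n = 20) | 80.9% | 76.5% |

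Like for like, the fall is about 4.4 points for each secondary outcome (80.5 − 76.1 and 80.9 − 76.5).

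**Step 4: can rounding close the gap at n = 18?**
- Relaxation, 1.25 to 1.35 s: 72.8% to 79.1%. The crossover mean of 1.34 s gives 78.5%.
- Grip, 2.25 to 2.35 kg with SD 2.5: 74.6% to 78.2%. If the approximate SD is also varied over 2.45 to 2.55 kg (my assumption), the range is 73.0% to 79.8%.

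Rounding of the differences alone does not recover the printed powers. Only the most favourable corner for grip comes within 0.2 points of 80%.

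**Step 5: differences detectable with 80% power at n = 18.** 1.37 s and 2.40 kg, about 5% and 4% above the printed differences.

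**Step 6: what a final 20 per arm requires.** 20/0.9 = 22.2, so 23 per arm and 46 in total (22 × 0.9 = 19.8 falls short). That is six more than the accrual limit.

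**Step 7: the planned model.** The secondary outcomes are to be analysed by repeated measures analysis of covariance with baseline as covariate. Assume equal variances at baseline and Month 6 and a correlation r between them, which the documents do not give. Baseline adjustment then multiplies the variance of the change score by (1 + r)/2. At n = 18, power for relaxation/grip is 82.5%/82.8% at r = 0.7, 80.3%/80.7% at r = 0.8 and 78.2%/78.6% at r = 0.9. It reaches 80% when r is about 0.81 (relaxation) or 0.83 (grip), or lower.

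**The case against.** **The secondary figures are covered in their own section.** The closing paragraph promises a final 20 per arm, which is the number those figures use, so 76% arises only if that paragraph is set aside. This is true, and it is why the printed powers are not wrong in themselves. But following that paragraph breaks the accrual limit of 40 and makes the primary statement's step from 18 to 20 pointless. Reading it as a restatement of that step leaves the secondary outcomes without the allowance for loss. Either way, a sentence has to change.

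**Eighteen per arm need not be the effective number.** Patients who stop drug are to be followed if willing, those who drop out are to be asked for a final evaluation, and the model uses all available data with baseline adjustment. This stands. A reader might infer that the trial is under-powered for its secondary outcomes, but the documents do not support that. As Step 7 shows, the planned analysis may fall on either side of 80%.

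**Other stronger readings that fail.**
- Setting 76% against the printed 82% suggests a loss of six points. On the same test the fall is about 4.4; the rest is rounding or approximation in the printed figure.
- The 60 in Table 3 might look like a third target. It equals the screening maximum in Study Population and is most likely a mislabelled screening total.
- The interim analysis might seem to inherit the ambiguity. Its trigger is an explicit count of 20 participants with 6 months of follow-up, so it needs no change on this account.

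**Conclusion.** The inconsistency is real and lies in current text. One rule accrues 40 and expects 18 per arm to remain. The other keeps 20 per arm, which means about 46 randomised at 10% loss. Under the first rule, t-test power for relaxation time and grip is 76.1% and 76.5%, not the 80.5% and 80.9% that 20 per arm would give. Under the second, the secondary statements hold within rounding and the stated enrolment is six too low.

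These figures assume the printed differences and SDs, two-sided 5%, exactly 10% loss in each arm, and no information from patients who withdraw. They describe the t-test that the protocol names for its power statements and not the planned model. Primary power is adequate under either rule. This is a consistency fault with a modest effect on two secondary power statements, worth correcting because the number randomised is a basic design quantity.

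**What to change.** State one enrolment rule and apply the same attrition basis to every power statement.

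**Simplest option: keep 40 randomised.** Delete the sentence promising a final 20 per arm. Restate secondary t-test power at 18 per arm as about 76% each, or as 80% for about 1.37 s and 2.40 kg. Add that the planned baseline-adjusted repeated-measures analysis may have more power, depending on a baseline-to-Month 6 correlation that the sponsor should supply. The cost is text only, plus a slightly less favourable stated figure.

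**Alternative: keep the final 20 per arm.** State the number randomised that it implies (about 46 at 10% loss) and align the Specific Aims, Trial Design and Study Population. The cost is about six more patients. Within the screening maximum of 60, the allowable screen-failure share would fall from 33% (20 of 60) to 23% (14 of 60).

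In either case, relabel the 60 in Table 3 as the number screened. This is a clerical correction.
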